- 1.2 18-month viral load will be assessed using blood draws taken during the 18-month assessment in the community (for microfinance group members) and at the facility (for non-microfinance group members).
- 2. For clinical secondary outcomes, we will measure systolic blood pressure and hemoglobin A1c at baseline and 18-months for all 900 microfinance group members enrolled in the trial. Blood pressure will be measured in the community by the clinical officer using a blood pressure arm cuff. HbA1c will be measured in the community by the clinical officers using a point of care test.
- 3. For non-clinical secondary outcomes, we will measure retention in care on an ongoing basis for all enrolled trial participants. Retention in care will be based on study records (REDCap) for intervention recipients and on medical records for facility care patients.
- 4. For exploratory outcomes and mediation analyses, we will collect survey data from all enrolled trial participants: at enrollment and 18-months for all trial participants, with an additional round of survey data collection at month 9 for all microfinance group members. Surveys will be administered by a research assistant to participants in a private location in-person. Surveys will assess demographics, health insurance enrollment and utilization, social support (Oslo Social Support Scale-3), quality of life (adapted version of the MOS-HIV scale), psychological distress (Patient Health Questionnaire-4), self-reported ART adherence (based on the adapted ACTG Adherence Questionnaire), self-reported adherence to NCD medications (based on the extent of DOSE-Nonadherence Questionnaire), barriers to accessing care, patient satisfaction with care, felt HIV stigma (9-item measure of felt stigma validated in Kenya). The survey instrument is included in Appendix III. For exploratory outcomes, we will collect data on microfinance group performance (e.g., saving and lending activities, loan default rates) for all microfinance group participants. Microfinance group performance data will be collected on a quarterly basis and recorded via REDCap. The microfinance data collection tool is included in Appendix IV.

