7.1.2 Follow up assessments

For study participants in MF groups (MF + ICB and MF+SOC), follow up assessments to evaluate primary and secondary outcomes will be conducted in the field at 9- and 18- months. During follow up assessments, MF group participants will:

- Provide a blood draw for HIV viral load testing (study month 18 only)
- Provide a systolic blood pressure reading (study month 18 only)
- Provide an HbA1c point of care test, if clinically indicated (study month 18 only)
- Complete the survey assessments (study month 9 and 18)

Trained research assistants will work with the clinical teams to collect survey assessment data on mobile tablets. Clinical teams will record blood pressure and HbA1c results in the patient's medical records and in the study REDCap records. At 18 months, clinical officers and research assistants will transport blood samples from the community to the Eldoret reference lab for analysis. For participants who do not attend MF group meetings during assessment time points (months 9 and 18), research assistants will use participant's contact information to schedule follow-up meetings to collect data if participants are willing to meet outside of the regularly scheduled MF meeting time. We will access and review AMRS for data on secondary outcomes (i.e., retention in care and chronic disease composite score).

For study participants receiving SOC (Study Arm C), follow up assessments to evaluate primary and secondary outcomes will be conducted at AMPATH facilities when the patient returns for their HIV clinic visit at 18-months. During follow up assessments, SOC patients will:

- Provide a blood draw for HIV viral load testing
- Complete the survey assessments

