7.2 Statistical analysis ⁶

The primary analysis of interest is comparing viral suppression at 18 months between the MF+ICB (Study Arm A) and MF+SOC groups (Study Arm B). As a secondary hypothesis, we will test MF+ICB vs SOC alone and MF+SOC vs SOC alone. To test both the primary and the secondary hypotheses we will use a generalized mixed effects model.³³ For the primary outcome, the model we will use is

$$log(P(Y_{ij}=1|I_j,S_j,VB_{ij},c_j)) = \beta_0 + \beta_1 I_j + \beta_2 S_j + \beta_3 VB_{ij} + c_j$$

⁶ See the Addendum to the overall project protocol starting on page 100 for changes made to the statistical analysis plan.

where, Y_{ij} is viral suppression at 18 months for participant i in cluster j, I_j is the indicator if cluster j is randomized to the MF+ICB arm, S_j is an indicator if cluster j comes from the SOC individuals, VB_{ij} is the baseline viral load for participant i in cluster j, and c_j is the random effect associated with cluster j. The estimator β_1 estimates the difference between the MF+SOC and MF+ICB arms and positive values indicate higher viral suppression in the MF+ICB arm. To test the primary hypothesis we will perform a hypothesis test for H_0 : $\beta_1 = 0$. To test the secondary hypothesis we will perform a hypothesis test for H_0 : $\beta_2 = 0$ and H_0 : $\beta_1 - \beta_2 = 0$.

For the secondary outcomes, we will modify the above model to reflect that retention in care is a proportion and the absolute mean change in systolic blood pressure and HbA1c level are each a continuous outcome. Dropout from the study will be handled using inverse probability weighting.³⁴ The design, analysis, and interpretation of the results from the trial will follow the recommendations given by the CONSORT statement on cluster randomized trials.³⁵ All data will be de-identified prior to the analysis phase.

- 8. Aim 2: Mixed methods to assess mechanisms through which MF and community-based care affect patient outcomes
- 8.1 Study Population and recruitment

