- 7. In each county, 10 group leaders from each of the 10 GISHE groups took turns selecting a raffle ticket.
- 8. The group leads then held onto their tickets until all the leads had picked their ticket.
- 9. Once all the leads had a ticket, the leads opened their tickets together and show them to the community attendees.
- 10. The raffle tickets were randomized into the respective Study Arms based on the label as aforementioned in 6a
- 11. Group leads were congratulated and given a chance to ask questions/seek any clarifications

Post Randomization

- 1. Project Manager communicated the randomization outcomes to the larger research team.
- 2. Group representative (group leads) present during the randomization communicated the randomization outcomes to their respective groups.
- 3. Align the Return to Care (RTC) dates for all the Study Arm A members.

10. The original Aim 1 analysis plan for the primary outcome (virologic suppression) that is summarized in section 7.2 of this protocol and in the published protocol ([name] BL et al. Integrated community-based HIV and non-communicable disease care within microfinance groups in Kenya: study protocol for the Harambee cluster randomised trial. BMJ Open. 2021 May 18;11(5):e042662. doi: 10.1136/bmjopen-2020-042662.) was revised. Details of the revised analysis plan, and reasons for the revision(s), are described in the following paragraphs.

Revised Analysis plan

Primary objective: Compare rates of viral suppression between the MF+ICB and MF+UC arms.

Secondary objective 1: Compare rates of viral suppression between the MF+ICB and UC arms.

Secondary objective 2: Compare rates of viral suppression between the MF+UC and UC arms.

Primary outcome definition: Achievement of HIV-1 RNA viral load suppression at 18-months. Participants whose 18-month viral load assessment occurred before January 1, 2023 were considered virologically suppressed if their viral load was <400 copies/mL. To adhere to changes to Kenya's national recommendations for HIV monitoring cutoffs that occurred during the trial, patients whose 18-month viral load assessment was on or after January 1, 2023 were considered suppressed if their viral load was <200 copies/mL.

Analysis set: The analysis set for all objectives is the intent-to-treat set and included all randomized participants for arms MF+ICB and MF+UC and all participants that in the UC arm that provided informed consent.

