Analysis plan for the primary objective: The analysis of the primary objective was conducted using a doubly robust generalized estimating equation with a logit link function accounting for potentially differential dropout as described in Prague M et al.⁷ The generalized estimating equation model included the intervention arm, used an independence working correlation matrix and the variance was estimated using a sandwich variance estimator for clustered data. The intervention effect was estimated using the log odds ratio coefficient of intervention in the generalized estimating equation. The primary hypothesis test of the intervention effect was conducted using a Wald test and 95% Wald-based confidence intervals were calculated.

Handling of dropout: Implementation of the method proposed in Prague M et al.⁷ relies on specifying a model for the dropout probability and two outcome models (one for each treatment arm). For the method to be a valid way to handle dropout, either the model for the dropout probability or both outcome models need to be correctly specified. The model used for the dropout probability was a logistic regression model with linear main effects of county, treatment arm, log(viral load at baseline+1)), schooling achieved, age, and gender. The model used for the outcome model in the MF+ICB was a logistic regression model with linear main effects of county, log(viral load at baseline+1)), schooling achieved, age, and gender and the model used for the outcome model in the MF+UC was a logistic regression model with linear main effects of county, log(viral load at baseline+1)), schooling achieved, monthly income, age, and gender. Monthly income was only used in one of the models due to instability of the model fitting when it was added to the other models. The dropout weights were well behaved with the largest weight being 1.42; therefore, we did not experience any extreme weights and hence made no adjustments to account for them.

Handling of missing data: Multiple imputation was used to account for missing data on baseline covariates and Rubin's rule for variance estimation was used for variance estimation.

⁷ Prague M, Wang R, Stephens A, Tchetgen Tchetgen E, DeGruttola V. Accounting for interactions and complex inter-subject dependency in estimating treatment effect in cluster-randomized trials with missing outcomes. *Biometrics*. Published online 2016. doi:10.1111/biom.12519

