11. The original definition of the Aim 1 secondary outcome (retention in care) that is summarized in section 3.4 of this protocol and in the published protocol ([name] BL et al. Integrated community-based HIV and non-communicable disease care within microfinance groups in Kenya: study protocol for the Harambee cluster randomised trial. BMJ Open. 2021 May 18;11(5):e042662. doi: 10.1136/bmjopen-2020-042662.) was revised. Specifically, the secondary endpoint was revised to be measured as a binary variable (rather than as a proportion). The revised endpoint defined a participant as always retained in HIV care if they attended at least one HIV care visit in each quarter a visit was scheduled, where attending a visit was defined as attending a visit within +/- 28 days of their scheduled visit date. This revision was made to prevent potential measurement bias between the study arms given that some community care recipients had more frequent care visits during the first 6 months of the trial as compared to facility (standard) care participants.

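### No stated analysis of the binary retention endpoint uses attendance before enrolment, which probably costs precision in the A-versus-B comparison

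*Combined protocol and SAP*

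**What the plan says.** Section 7.2 defines a log-link mixed model for viral suppression with arm indicators, baseline viral load and a random group effect. For retention it says only: "For the secondary outcomes, we will modify the above model to reflect that retention in care is a proportion". Addendum item 11 then makes retention binary. A participant counts as retained if "The revised endpoint defined a participant as always retained in HIV care if they attended at least one HIV care visit in each quarter" with a scheduled visit, allowing 28 days either side. Item 11 gives a reason for the change (unequal visit frequency between arms) but no analysis model.

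Addendum item 10 is a full revised plan, but its scope is "The original Aim 1 analysis plan for the primary outcome (virologic suppression) that is summarized in section 7.2". Its two secondary objectives are viral suppression against usual care, not retention. Its covariates are county, log baseline viral load, schooling, age and gender, with arm in the dropout model and monthly income in one outcome model.

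On data sources, section 7.1.2 says of microfinance members: "We will access and review AMRS for data on secondary outcomes", and it names retention among them. Section 7.1 says: "Retention in care will be based on study records (REDCap) for intervention recipients and on medical records for facility care patients".

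**The concern.** A baseline measure of the outcome is usually the strongest covariate available, and the other outcomes have one. Viral suppression is modelled with baseline viral load, and systolic pressure and HbA1c are analysed as change from baseline. Retention has no counterpart. Its one named covariate, baseline viral load, is likely to predict attendance weakly in a population that item 10 describes as having a high rate of suppression.

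Whole groups were randomised, 57 in all. Chance differences between groups in habitual attendance therefore remain in the arm comparison and widen its interval. The documents give no power or precision figure for retention, so nothing shows that there is precision to spare.

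**Working it through.** **1. The plan's own figure.** The only power statement (section 3.4.2) is for viral suppression: above 80% for a 15% increase. It reproduces if 15% means percentage points.
- Inputs: 20 groups per arm, 450/20 = 22.5 per group, 15% dropout, ICC 0.05, SD of group size 5, two-sided 0.05.
- m = 22.5 × 0.85 = 19.125; CV = 5/22.5 = 0.222.
- Design effect = 1 + [(1 + CV²)m − 1] × 0.05 = 1.953.
- Effective n per arm = 20 × 19.125 / 1.953 = 195.8.
- Power is 0.917 at a control rate of 20%, 0.854 at 50%, with a minimum of about 0.846 near 42.5%.

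This says nothing about retention.

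**2. Which retention analysis is stated.** Section 7.2 names one baseline covariate, item 10 covers viral suppression only, and item 11 names no model. None of them lists prior attendance.

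**3. Whether the covariate can be obtained.** Section 3.3.1 requires current AMPATH HIV care, an AMRS ID, consent to AMRS access, and ART started at least 6 months before enrolment. That guarantees about two quarters of history. Sections 6.2 and 7.1 already read the record over the 12 months before enrolment for baseline viral load. Prior attendance is thus largely reachable, but no section says that scheduled and attended dates are held for everyone.

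**4. Simple bound.** With correlation r between prior attendance and the outcome, variance is multiplied by 1 − r² and the SE by √(1 − r²). The documents give no r.

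| r | variance × | SE × | power, assumed 70% vs 80%, n = 195.8 |
|---|---|---|---|
| 0 | 1.00 | 1.000 | 0.628 |
| 0.2 | 0.96 | 0.980 | 0.646 |
| 0.3 | 0.91 | 0.954 | 0.669 |
| 0.5 | 0.75 | 0.866 | 0.753 |

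**5. Simulation with groups.** Assumptions: 56 groups of 16; six follow-up quarters; a stable attendance tendency per person and per group, normal on the logit scale; person SD 1.0-1.5; group SD 0.2-0.5; mean quarterly attendance 90%. The comparator is the arm difference with no covariate.
- Two prior quarters: variance falls about 6-21%. Interval width is multiplied by √0.94 = 0.97 to √0.79 = 0.89.
- Four prior quarters: variance falls about 11-32%. Interval width is multiplied by √0.89 = 0.94 to √0.68 = 0.82.
- At person SD 0.5 with two quarters, the reduction is only about 0.5-7%.

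The risk-difference and log-link scales agree. The simple bound understates the gain when groups differ. With person SD 1.0, group SD 0.5 and four quarters, r is 0.28, so r² = 0.08, yet variance falls by about 25%. The covariate also removes imbalance between groups.

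**6. The scale matters.** In a separate simulation (20 groups of 22 per arm; prior attendance 80-90%, retention 70%), the SE of the log odds ratio was compared three ways.

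| setting | unadjusted | marginal, adjusted | covariate in conditional logit |
|---|---|---|---|
| prior 90%, phi 0.26 | 0.205 | 0.192 | 0.206 |
| prior 80%, phi 0.45 | 0.194 | 0.162 | 0.207 |

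A conditional logit does not shrink the SE, because its estimand moves away from zero. Its power still stayed level or rose in every setting examined (for example 0.70 to 0.85).

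**The case against.** **The covariate is not shown to be excluded.** A reader might infer that the revised endpoint was analysed without prior attendance. The documents do not say so. No explicit model exists for the binary endpoint, and section 7.2 promises only an adapted model. What stands is that no stated analysis uses it.

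**The data are not all in one record.** A reader might also infer that a single medical record holds both outcome and baseline. In fact Arm A's follow-up retention comes from REDCap. The section 2 schedule lists facility visits for Arm B participants at non-AMRS sites, and section 4.2 lists members' AMRS ID as available only for some. This stands as a limit on completeness. It does not remove the covariate: before randomisation Arm A members were ordinary facility patients, so the REDCap source concerns follow-up only.

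**The gain may be small.** Members must already be in HIV care and attend group meetings consistently, which may compress variation in attendance. This stands, and it pulls the gain towards the low end.

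**Collapsing to yes/no does not make the missing adjustment more costly.** That inference is tempting but unsupported. In simulation at person SD 1.0 and 90% attendance, adjustment recovered less for the binary endpoint than for the proportion (12% against 19%, and 26% against 37%). Item 11 also gives a measurement reason for the binary form.

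**It may be too late.** The addendum's analysis account is in the past tense and refers to a main manuscript. A covariate added after retention has been analysed would be post hoc. This stands and governs how the result should be labelled.

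**Conclusion.** The point holds as a missed gain in precision on a secondary endpoint. It is not a bias or a validity error. At 90% quarterly attendance the variance of the A-versus-B effect would fall by about 6-21% with two prior quarters and 11-32% with four, on a risk-difference or risk-ratio scale.

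These figures assume a stable attendance tendency, person SD 1.0-1.5 and group SD 0.2-0.5, and they are measured against no adjustment at all. They shrink if attendance varies little, if habits change after randomisation, or if baseline viral load already carries some of the information. The documents supply none of these quantities, so the range is illustrative. The absence of any explicit model for the binary endpoint is certain from the text and needs correcting whatever the gain.

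**What to change.** 1. State the model for the binary retention endpoint.
2. Apply the item 11 rule to AMRS or facility visits in the 12 months before randomisation, or from ART start if shorter. This gives the share of scheduled quarters attended. Extract it the same way in both randomised arms.
3. Include that share in the A-versus-B analysis through a marginal estimator, such as the item 10 doubly robust GEE with the share in the outcome models, or as a covariate under the section 7.2 log link. Do not rely on a conditional logit to narrow the interval.
4. Handle missing values with the multiple imputation that item 10 already uses for baseline covariates.
5. Leave the share out of the Arm C contrasts by default. For members it is measured after they joined microfinance, so adjusting could remove part of the effect of interest.
6. If retention has already been analysed, report the result as a labelled sensitivity analysis.

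Cost: a short addition to the analysis plan and one extra record extraction, with nothing new asked of participants. Members at non-AMRS sites would need on-site record checks. These are currently listed for Arm B only, so any in Arm A would be additional fieldwork.
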